6.1.2 Ancillary treatments

Mild to moderate infusion related reactions have been reported in VAY736 clinical trials of autoimmune diseases. For the first two infusions, premedication for the risk of infusion reactions is required. Premedications should be administered 30 minutes to 2 hours prior to each of the first two infusions of VAY736 and should include oral acetaminophen 1,000 mg (or equivalent), oral or intravenous antihistamine, and intravenous corticosteroid (prednisolone 100 mg or equivalent) or similar prophylaxis based on institutional guidelines. For subsequent infusions

(infusions three and beyond), premedication may be administered if deemed appropriate by the treating physician.

Acute allergic reactions should be treated as needed per institutional standard of care. In the event of anaphylactic/anaphylactoid reactions, this includes any therapy necessary to restore normal cardiopulmonary status. If a patient experiences a Grade ≥ 3 anaphylactic/anaphylactoid reaction, the patient will be discontinued from the study. The CTCAE category of “Infusion related reaction” should be used to describe study treatment related infusion reactions, unless the investigator considers another category, such as “Allergic reaction,” “Anaphylaxis,” or “Cytokine release syndrome” more appropriate in a specific situation.

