6.1.5 Treatment duration

Patients will receive VAY736 and ibrutinib in combination for up to a total of six cycles. Patients will continue on VAY736 and ibrutinib therapy for Cycle 7 and Cycle 8 if the patient has evidence of disease at the radiological assessment or abnormal blood counts defined by IWCLL response criteria at C6D15. Starting with C7D1, VAY736 will be discontinued if the patient has no evidence of disease in radiological assessment and normal blood at C6D15 and ibrutinib will be administered for the next two cycles. [REDACTED]

[REDACTED] Further treatment with ibrutinib is dependent upon the outcome of the assessment that is conducted at C9D1 (see [Section 7.1.2](#)).

Patients may be discontinued from treatment with the study drug(s) earlier due to unacceptable toxicity, disease progression and/or at the discretion of the investigator or the patient. Patients, who discontinue VAY736 for reasons other than disease progression prior to 6 cycles of treatment, may continue with ibrutinib through the C9D1 assessment. Patients who discontinue ibrutinib for reasons other than disease progression prior to 6 cycles of treatment may continue with VAY736 through cycle 6 and have a disease assessment at C9D1. Patients who have disease progression and who have evidence of clinical benefit, such as disease shrinkage at other sites or symptomatic improvement, may continue treatment with the agent(s) being administered at the time disease progression is recorded. In addition, treatment may be temporarily interrupted to permit local therapy for symptomatic metastases after disease progression has been documented. Patients who continue on treatment after disease progression should discontinue study treatment once they are no longer deriving benefit as assessed by the investigator.

A patient who has experienced an interruption of more than 28 days of either one or both drugs may remain on study if the patient has experienced clinical benefit and the investigator believes it is in the best interest of the patient to remain on study and such action is agreed to by Novartis. Both the decision and documentation of the discussion with Novartis, must be available in the source documentation and described as an investigator comment in the eCRF.

[REDACTED]

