6.3.1.3 VAY736 and ibrutinib

Any dose changes must be recorded on the Dosage Administration Record eCRF.

If a patient requires a dose interruption of > 28 days of either VAY736 or ibrutinib from the intended day of the next scheduled dose, then the patient must be discontinued from the study unless otherwise specified in [Section 6.1.5](#). Patients who discontinue the study for a study related adverse event or an abnormal laboratory value must be followed as described in [Section 6.3.2](#).

Table 6-4 Criteria for dose reduction / interruption and re-initiation of VAY736 treatment for adverse drug reactions.

Dose modifications for VAY736	
Worst toxicity CTCAE Grade ^a (value) during a cycle of therapy	
Investigations (Hematologic)	
Neutropenia (ANC)	
Grades 1 -3	Maintain dose level
Grade 4 (ANC < 500/mm3)	Hold VAY736 until ANC $\geq 0.5 \times 10^9/L$, then resume VAY736 at same dose levels (with G-CSF support) or lower dose levels at investigator discretion.
Thrombocytopenia	
Grade 4 (PLT < 25,000/mm3)	Hold VAY736 until \leq Grade 3 then resume VAY736 at same dose levels or lower dose levels at investigator discretion
Febrile neutropenia (ANC < $1.0 \times 10^9/L$, fever $\geq 38.5^{\circ}C$)	Hold VAY736 until ANC $\geq 0.75 \times 10^9/L$, then resume VAY736 at same dose levels (with G-CSF support) or lower dose levels at investigator discretion.
Investigations (Renal)	
Serum creatinine	
Grade 1 (> ULN - 1.5 x ULN)	May maintain dose level
Grade 2 (> 1.5 - 3.0 x ULN)	Delay study treatment until resolved to Grade 1 or baseline If resolved by ≤ 7 days maintain dose level If resolved ≥ 7 days reduce one dose level
Grade 3 (> 3.0 - 6.0 x ULN)	Delay study treatment until resolved to Grade 1 or baseline If resolved by ≤ 7 days maintain dose level If resolved ≥ 7 days reduce dose of VAY736
Grade 4 (> 6.0 x ULN)	Omit dose and discontinue patient from study drug treatments
Investigations (Hepatic)	
Isolated total Bilirubin elevation	
> ULN – 1.5 x ULN	Maintain dose level
> 1.5 - 3.0 x ULN	Omit dose. Monitor LFTs ^b weekly, or more frequently if clinically indicated, until resolved to $\leq 1.5 \times$ ULN. If resolved in ≤ 7 days, then maintain dose level If resolved in > 7 days, then $\downarrow 1$ dose level

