Grade 2	Maintain dose level, but initiate/intensify appropriate skin toxicity therapy (such as antihistamines, topical corticosteroids and low-dose systemic corticosteroids)
Grade 3, despite skin toxicity therapy	Omit dose until resolved to Grade \leq 1, then: If resolved in \leq 7 days, then \downarrow 1 dose level If resolved in $>$ 7 days (despite appropriate skin toxicity therapy), then discontinue patient from study drug treatment
Grade 4, despite skin toxicity therapy	Omit dose Discontinue patient from study drug treatment
Infusion Reaction	
Grade 1	Decrease infusion rate until recovery
Grade 2	Stop infusion Before restarting – pre-medicate as outlined in Section 6.1.2 . Restart infusion at 50% of previous rate under continuous observation. Ensure that there is a minimum observation period of 1 hour prior to restarting the infusion(s) If the AE recurs at the reinitiated slow rate of infusion, and despite pre-medication, then discontinue patient from study
Grade 3 or 4	Discontinue treatment
Other adverse events	
Grade 1 or 2	Maintain dose level
Grade 3 or 4	Hold VAY736 until resolved to \leq Grade 1 or baseline. If toxicity resolves within 7 days, resume at the same dose. If treatment delay is $>$ 7 days and \leq 28 days, restart at lower dose level of the VAY736. If delay is greater than 28 days, discontinue treatment.

All dose modifications should be based on the worst preceding toxicity.

^a Common Toxicity Criteria for Adverse Events (CTCAE Version 4.03)

^b Core LFTs consist of ALT, AST, GGT, total bilirubin (fractionated [direct and indirect], if total bilirubin > 2.0 x ULN), and alkaline phosphatase (fractionated [quantification of isoforms], if alkaline phosphatase > 2.0 x ULN.)

^c "Combined" defined as total bilirubin increase to the defined threshold concurrently with ALT/AST increase to the defined threshold

If combined elevations of AST or ALT and total bilirubin do not meet the defined thresholds, please follow the instructions for isolated elevation of total bilirubin and isolated elevation of AST/ALT, and take a conservative action based on the degree of the elevations (e.g. discontinue treatment at the situation when omit dose is needed for one parameter and discontinue treatment is required for another parameter). After all elevations resolve to the defined thresholds that allow treatment re-initiation, re-start the treatment either at the same dose or at one dose lower if meeting a criterion for dose reduction

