Patients who discontinue one of the combination drugs (ibrutinib or VAY736) prior to six cycles of treatment for reasons other than disease progression may continue the other drug until the end of treatment period (VAY736 until C6D28 or ibrutinib until C8D28). All patients regardless of study treatment duration, who have not progressed, will have a final disease assessment at C9D1 (end of treatment period).

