7.1.3 Discontinuation of study treatment

Patients who discontinue study treatment (as defined in [Section 7.1.2](#)) on or before C9D1 for any reason will have an EOT visit and assessments conducted within 14 days of the last dose of study treatment or within 14 days of the decision to discontinue study treatment, see [Table 7-1](#) or [Table 7-2](#) for assessments to be conducted.

During the study treatment period (defined in [Section 7.1.2](#)), patients will be monitored to assess safety and any anti-tumor activity of the treatment.

Patients may voluntarily discontinue from the study treatment for any reason at any time. If a patient decides to discontinue from the study treatment, the investigator should make a reasonable effort (e.g. telephone, e-mail, letter) to understand the primary reason for this decision and record this information in the patient's chart and on the appropriate CRF pages. They may be considered withdrawn if they state an intention to withdraw, fail to return for visits, or become lost to follow-up for any other reason.

Study treatment must be discontinued under the following circumstances:

- Adverse events, that results in a significant risk to the patient's safety.
- The following deviation from the prescribed dose regimen for study treatment: dose interruption of > 28 days from the intended day of the next scheduled dose, unless otherwise specified in [Section 6.1.5](#).
- Pregnancy
- Any other protocol deviation that results in a significant risk to the patient's safety
- Study terminated by Novartis
- Patient/guardian decision

Patients who have achieved a CR may discontinue treatment at investigator discretion.

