For patients who discontinue treatment for reasons other than documented disease progression, death, lost to follow-up, or withdrawal of consent, tumor assessments must continue to be performed as outlined in [Table 7-1](#) or [Table 7-2](#), as appropriate for the dosing regimen of VAY736, until documented disease progression, death, lost to follow-up, or withdrawal of consent.

[Table 7-2](#).

([Hallek et al 2018](#)). As such, patients will be defined as having [REDACTED] if they have blood or marrow with <1 CLL cell per 10,000 leukocytes.

Table 7-3 Disease assessment collection plan

Procedure	Screening/baseline	During treatment/follow-up
CT or MRI with contrast enhancement (Chest, Abdomen, Pelvis)	Mandated	Refer to Table 7-1 or Table 7-2 , as appropriate for VAY736 dose regimen.
[REDACTED]	[REDACTED]	[REDACTED]

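### Three stopping rules take a non-progressed patient off the study, although Protocol 7.1.2 and 7.2.1 require that patient to be assessed at C9D1 and followed for progression

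*Protocol*

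**What the plan says.** Three rules end participation.

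- Protocol 6.1.2: after a Grade 3 or worse "anaphylactic/anaphylactoid reaction, the patient will be discontinued from the study".
- Protocol Table 6-4, Infusion Reaction, Grade 2: "If the AE recurs at the reinitiated slow rate of infusion, and despite pre-medication, then discontinue patient from study".
- Protocol 6.3.1.3: after more than 28 days without either drug, for whatever reason, "then the patient must be discontinued from the study unless otherwise specified in" Section 6.1.5. That section says such a patient "may remain on study if the patient has experienced clinical benefit", the investigator judges it to be in the patient's interest, and the sponsor agrees.

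Two rules keep the same patient under assessment.

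- Protocol 7.1.2: "All patients regardless of study treatment duration, who have not progressed, will have a final disease assessment at C9D1".
- Protocol 7.2.1 takes patients who stop treatment for a reason other than progression, death, loss to follow-up "or withdrawal of consent, tumor assessments must continue to be performed as outlined in" the visit schedule, "until documented disease progression, death, lost to follow-up, or withdrawal of consent".

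Protocol 7.1.3 lists, among reasons to stop study treatment (not the study), a "dose interruption of > 28 days from the intended day of the next scheduled dose, unless otherwise specified in" Section 6.1.5.

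**The concern.** A site with a non-progressed patient who meets one of the three rules has two instructions that cannot both be followed. If it takes the patient off the study, three things follow in the analysis.

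- The C9D1 response is missing. SAP 2.6.2 counts a treated patient without end-of-treatment response information as a non-responder and keeps the patient in the CR/CRi and ORR denominators.
- TTP is censored at the last adequate assessment (Protocol 10.5.2, SAP 2.8.1).
- SAP 5.2.2.3 adopts a treatment-policy strategy and uses tumor data collected after treatment stops for best overall response. Those data are never collected.

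The 28-day rule has a further problem. Read literally, 6.1.5 lets a patient stay on study only with clinical benefit, so retention depends on outcome. Patients doing less well would be the ones censored, which tends to lengthen estimated TTP.

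**Working it through.** **Text comparison**

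| Situation | Wording that removes the patient | Wording that stops drug only or keeps the patient |
|---|---|---|
| Infusion reaction | Table 6-4 Grade 2, recurrent: off study | Table 6-4 Grade 3 or 4: treatment stops |
| Grade 3 or worse anaphylaxis | 6.1.2: off study | 6.1.5: a patient who stops VAY736 without progression may continue ibrutinib through C9D1 |
| Interruption over 28 days | 6.3.1.3: off study unless 6.1.5 applies | 7.1.3: study treatment stops, same trigger and same exception |
| Any non-progressed patient | none | 7.1.2: C9D1 assessment; 7.2.1: tumor assessments continue |

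Read literally, a recurrent Grade 2 reaction has a harsher disposition than a Grade 4 one. The other permanent-stop rows of Table 6-4 stop drug only and are not at issue.

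**Effect of one lost responder on the CR/CRi summary**

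Inputs: the SAP 2.8.1 prior Beta(0.25, 1) and N = 20 per arm (SAP 3.1.2). The posterior is Beta(0.25 + x, 1 + 20 − x) with mean (0.25 + x)/21.25.

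SAP Table 3-2 reproduces: x = 8 gives mean 8.25/21.25 = .388, 90% credible interval .224 to .565 and P(rate ≥ 40%) = .443; x = 6 gives P(rate < 20%) = .170.

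- 8/20 to 7/20: mean 7.25/21.25 = .341, interval .185 to .515, P(rate ≥ 40%) = .274.
- 6/20 to 5/20: P(rate < 20%) rises from .170 to .332.

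Both shifts assume that the removed patient would have been CR/CRi at C9.

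**How often this could happen**

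The documents give no removal rate. The nearest figure is in the Amendment 03 rationale, which names a Grade 2 infusion-related reaction among 11 treated patients. Taken as one patient, 1/11 = 9.1%, exact 95% CI 0.2% to 41.3%. Let r be the chance that such a reaction recurs on slowed restart (assumed, 0 to 50%). The per-patient removal probability from this row alone is p = r/11.

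| r | p | expected in 20 (20p) | P(at least one) = 1 − (1 − p)^20 |
|---|---|---|---|
| 0 | 0 | 0 | 0 |
| .25 | .0227 | 0.45 | .369 |
| .50 | .0455 | 0.91 | .606 |

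If the chance that a removed patient would have been CR/CRi is 10% to 20% (assumed), the expected number of lost responders per arm at r = .50 is 0.91 × .10 = 0.09 to 0.91 × .20 = 0.18. At the upper confidence limit for the reaction rate, .413 × .50 × 20 = 4.1 removals and 4.1 × .20 = 0.8 lost responders, so the data do not bound the rate tightly. Anaphylaxis and 28-day interruptions would add to this at unknown rates.

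**TTP**

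A patient last assessed at C6D15 is censored at day 5 × 28 + 15 = 155. If kept, the same patient could be followed from C9D1 (day 8 × 28 + 1 = 225) for two years, to about day 955. The loss is the follow-up after day 155. Earlier risk sets still include the patient: with 20 patients and one event at day 100, the Kaplan-Meier estimate at six months (day 183) is 19/20 = .950, against 18/19 = .947 if the patient were dropped entirely.

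**The case against.** The strongest reply is that the word study is loose drafting and that the protocol shows what was meant. Section 7.1.3 gives the same 28-day trigger as a treatment stop; 6.1.5 sits under a heading about treatment duration; the title of Table 6-4 concerns VAY736 treatment; and 6.3.1.3 sends such patients to the toxicity follow-up in 6.3.2, which is written for patients whose treatment is interrupted or stopped. Section 4.1 gives C9D1 to patients who have remained on study, which can be read as reconciling the texts. Much of this stands, and the intended meaning is probably a treatment stop. It does not remove the conflict. Sections 7.1.2 and 7.2.1 carry no such limit, the same sentence in 4.1 includes patients who stopped treatment for reasons other than progression, and 6.3.2 covers toxicity rather than disease assessment.

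The reply is also right on size. The posterior shifts need a removed patient who would have responded. That is hard to square with the 28-day route, where those removed lack clinical benefit, and is not the expected case in Arm A, where patients had no CR after more than a year of ibrutinib.

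A reader might infer that 7.1.5 closes these patients out at 30 days. It gives two times for completing the end-of-study form, after the 30-day safety period or at progression in efficacy follow-up, and does not say which applies here; the 30-day close-out is only a possibility.

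**Conclusion.** The conflict is real and stands in current operative text, but it is a minor point. It rests on a site following the off-study wording literally; 7.1.3 and 4.1 suggest that this was not intended. If followed, it costs the C9D1 response, later tumor data and TTP follow-up, and in the 28-day case ties retention to clinical benefit.

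The effect is confined to secondary anti-tumor endpoints; MTD estimation uses Cycle 1 DLTs and is not touched. The removal rate is unknown. The shift from .443 to .274 shows what one lost responder would do, not what is expected.

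Two stronger readings are not supported. A reader might infer that the rules have removed patients and biased the results; the documents report no such removal. A reader might also infer that a patient censored early adds nothing to the 6- to 24-month TTP rates; as shown, the patient still counts in earlier risk sets and only adds no follow-up after censoring.

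Prospective reach is small. The SAP Introduction records early termination endorsed on 22-Sep-2023, and the rules act during dosing or drug interruption, so patients past C9D1 are no longer exposed to the infusion rules.

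**What to change.** - In 6.1.2 and the Grade 2 infusion-reaction row of Table 6-4, discontinue VAY736 rather than the study, and note that ibrutinib may continue per 6.1.5 and 7.1.2. Writing study treatment here would be wrong: the protocol glossary and SAP 2.1.1.1 define it as both drugs, so it would stop ibrutinib for a VAY736 infusion event, whereas 6.3.1.2 exempts infusion reactions even from the rule to hold ibrutinib.
- In 6.3.1.3, discontinue study treatment, matching 7.1.3.
- In 6.1.5, apply the clinical-benefit condition to remaining on treatment, not to remaining on study.
- Add one sentence: *These patients remain on study for the C9D1 and TTP assessments per 7.1.2 and 7.2.1.*

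No SAP rule changes. The summary of reasons for study discontinuation already planned in SAP 2.6.2 can be used to look for removals of this kind.

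The cost is a wording change in four places and one added sentence. Any patient who would otherwise have been removed would have the C9D1 assessment and up to two years of follow-up, with visits every three months and CT every six. Sections 7.1.2 and 7.2.1 already require these. No safety protection is lost, because VAY736 still stops in the infusion cases and study treatment still stops in the 28-day case.

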6.3.2 Follow-up for toxicities

Patients whose treatment is interrupted or permanently discontinued due to an adverse event or clinically significant laboratory value, must be followed up at least once a week (or more frequently if required by institutional practices, or if clinically indicated) for 4 weeks, and subsequently at approximately 4-week intervals, until resolution or stabilization of the event, whichever comes first. Appropriate clinical experts such as ophthalmologist, endocrinologist, dermatologist, psychiatrists etc. should be consulted as deemed necessary.

Table 6-5 outlines the follow-up evaluation recommended for toxicities of specific types and CTCAE grades.

Table 6-5 Follow-up evaluations for selected toxicities

TOXICITY	FOLLOW-UP EVALUATION
Blood and lymphatic system disorders	If CTCAE Grade 4 neutropenia, thrombocytopenia or anemia, or febrile neutropenia occurs, test pertinent labs at least weekly until resolution to baseline or stabilization.
Hepatic	If a hepatic adverse event occurs, ALT, AST and total bilirubin must be measured at least once a week until resolution to CTCAE Grade \leq 1 or baseline. In patients with total bilirubin Grade \geq 2 (any duration) bilirubin should be fractionated into total/direct or indirect/direct components and any additional evaluation as clinically indicated by these results should be performed
Investigations (metabolic)	Test twice weekly until \leq CTCAE grade 2, continue to test weekly until resolution to \leq CTCAE grade 1 or stabilization. Amylase or lipase \geq CTCAE grade 3 A CT scan or equivalent imaging procedure to assess the pancreas, liver, and gallbladder is recommended within 7 days of the first occurrence of any \geq CTCAE grade 3 result, to exclude disease progression or potential other liver disease. In patients with serum triglycerides \geq 500 mg/dL, urine amylase also needs to be tested.
Cardiac disorders QT and ECG ECG changes indicative of ischemic event	Twice weekly ECGs until normalization or stabilization of ECG findings

6.4 Concomitant medications

6.4.1 Permitted concomitant therapy

The patient must be told to notify the investigational site about any new medications he/she takes after the start of the study drug. All medications (other than study drug) and significant non-drug therapies (including physical therapy, herbal/natural medications and blood transfusions) administered during the study must be listed on the Concomitant Medications or the Procedures and Significant Non-Drug Therapies CRF.

The use of growth-factor support (e.g. filgrastim, pegfilgrastim, erythropoietin, or darbepoetin) should follow standard practice according to product information and per institutional guidelines. Growth factors should not be administered to allow for patient eligibility at screening. Blood/platelet transfusions, the use of bisphosphonates and topical steroid products, and daily corticosteroid use of ≤ 10 mg/day prednisone (or equivalent) is permitted at the discretion of the treating physician. Therapeutic doses of anticoagulant will not be permitted. Low doses of warfarin for line patency are allowable.

Limited-field palliative radiotherapy to non-target lesion(s) may be allowed as concomitant therapy following a documented discussion with Novartis. Such local therapies administrated during the study treatment must be listed on the Concomitant radiotherapy/surgery case report form (CRF) page.

